2. STATISTICAL METHODS

2.1. Study Endpoints

The co-primary endpoints are:

- Safety as assessed by adverse events (AE)s, vital signs, electrocardiograms (ECG)s, and clinical laboratory tests (includes patients with HSCT-TMA, aHUS, and TTP)
- For HSCT-TMA patients, response to OMS721 treatment. A responder is defined as a patient with HSCT-TMA who demonstrates improvement in laboratory TMA markers (platelet count and LDH) and clinical benefit (either improvement in organ function or reduction in transfusion burden). The specific criteria are defined as follows:
 - Improvement in laboratory TMA markers:
 - Platelet count:
 - For patients with baseline platelet count $\leq 20,000/\mu\text{L}$:
 - Tripling of baseline platelet count
and
 - Post-baseline platelet count $> 30,000/\mu\text{L}$
and
 - No platelet transfusions 2 days before and on the day of the platelet count collection
 - For patients with baseline platelet count $> 20,000/\mu\text{L}$
 - Increase in platelet count $\geq 50\%$
and
 - Post-baseline platelet count $> 75,000/\mu\text{L}$
and
 - No platelet transfusions 2 days before and on the day of the platelet count collection
 - and
 - LDH:
 - LDH < 1.5 x upper limit of normal (ULN)

and

- Improvement in clinical status:
 - Improvement in organ function as evidenced by any of the following:
 - Improvement in renal function:
 - Reduction of creatinine > 40%
 - or
 - Creatinine < ULN and reduction of creatinine > 20%
 - or
 - Discontinuation of renal replacement therapy (RRT),
 - or**
 - Improvement in pulmonary function:
 - Extubation and discontinuation of ventilator support
 - or
 - Discontinuation of non-invasive mechanical ventilation (continuous positive pressure ventilation)
 - or**
 - Improvement in neurological function:
 - Improvement in reversible neurological conditions (e.g., cessation of seizures)
 - or
 - Stabilization of irreversible neurological conditions (e.g., stability of neurological deficits following stroke without further deterioration or subsequent strokes)
 - or**
 - Improvement in gastrointestinal function (gastrointestinal HSCT-TMA will require diagnosis by tissue biopsy):
 - Improvement measured by improvement in the gastrointestinal measures in the Mount Sinai Acute GVHD International Consortium (MAGIC) criteria
 - or**

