 - Freedom from transfusion (no transfusions for at least 4 weeks from the last transfusion except for patients who died within 4 weeks of the last transfusion, only evaluated in patients who received transfusions within the 2 weeks prior to or on the first OMS721 dose date).

The secondary endpoints of this study are to evaluate the following in patients with HSCT-TMA treated with OMS721:

- Duration of response defined as the number of days from the first response date to the first relapse date
- 100-day survival, from the date of TMA diagnosis
- Overall survival, from the date of TMA diagnosis
- Freedom from platelet transfusion defined as no platelet transfusions for at least 4 weeks following the last platelet transfusion except for patients who died within 4 weeks of the last platelet transfusion (only evaluated in patients who had platelet transfusions in the 2 weeks prior to or on the first OMS721 dose date)
- Freedom from RBC transfusion defined as no RBC transfusions for at least 4 weeks following the last RBC transfusion except for patients who died within 4 weeks of the last RBC transfusion (only evaluated in patients who had RBC transfusions in the 2 weeks prior to or on the first OMS721 dose date)
- Change from baseline in platelet count (post-baseline platelet counts without platelet transfusions 2 days before and on the day of the platelet count collection will be used) over time using central laboratory values
- Change from baseline in LDH over time using central laboratory values
- Change from baseline in haptoglobin over time using central laboratory values
- Change from baseline in Hgb (post-baseline Hgb without RBC and whole blood transfusions 6 days before and on the day of the Hgb collection will be used) over time using central laboratory values
- Change from baseline in creatinine over time using central laboratory values

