2.8.2. Efficacy Analyses

2.8.2.1. Primary Efficacy Endpoint

A patient is a responder if this patient meets the responder criteria (Section 2.1) at any time post-baseline during the study. If a patient is not evaluable for a response criterion due to confounding factors, the non-evaluable response criterion will not be included in the determination of responder. Evaluability of each response criterion will be determined by a clinical review of relevant data and will be documented in the clinical study report. For example, potential confounding factors include graft failure for platelet count or transfusions, and nephrotoxic medications for renal function. Furthermore, laboratory values collected from both the local laboratories and the central laboratories will be used to determine response status.

Analysis of the primary efficacy endpoint will use a non-responder imputation to impute missing or incomplete data to evaluate response. The number and percent of responders will be summarized with exact 95% CI (Clopper-Pearson) by dose and total for the FAS and PAS

populations. If the lower bound of the exact 95% CI is greater than 15%, there is sufficient evidence to demonstrate efficacy of narsoplimab in the target patient population. Each criteria of the response will be listed for each patient.

Sensitivity analyses will include:

1. Subgroup analyses for the following subgroups will be performed for the FAS population:
 - Age (< 65 , ≥ 65 years)
 - Gender (Male or Female)
 - Graft-versus-host disease (GVHD) (Yes or No)
 - Significant infection (Yes or No)
 - Graft failure or non-engraftment (Yes or No)
 - Female-to-male transplant (Yes or No)
 - Multiple organ TMA involvement (Yes or No)
 - Mismatched donor (Yes or No)
 - Baseline platelet counts ($< 20,000$ or $\geq 20,000$ platelets/ μL)
 - Renal dysfunction at baseline (Creatinine $> \text{ULN}$ or spot urine protein $\geq 2+$ or > 30 mg/dL; Yes or No)
 - Any transfusions within the 2 weeks prior to or on the first OMS721 dose date (Yes or No)
2. A completer analysis will be performed using the patients with non-missing responses only. Exact 95% CI for the completer response rate will be provided for the FAS population by dose.
3. Two alternative definitions of response will be analyzed:

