3.4. Analysis of Safety Endpoints

3.4.1. Clinical Adverse Events

Adverse events collected during the study and significant AEs will be combined for analysis. They will be labeled as adverse events for simplicity. Significant AEs are the AEs that occurred outside the protocol-specified reporting period and will be collected for the HSCT-TMA patients only. For reporting purposes, AEs will be divided into 2 categories:

1. Those that occurred prior to the start of study treatment (pre-treatment events) and
2. Those that occur or worsen in intensity after the start of study treatment (treatment-emergent adverse events).

Summary of AEs will include the non-serious AEs during the AE evaluation period and all reported serious AEs. The AE evaluation period is defined from the time of informed consent to 37 days after the last study drug administration.

All AEs will be classified by system organ class and preferred term using the Medical Dictionary for Regulatory Activities (MedDRA). An AE is considered treatment related if the relationship to study drug is either probable or possible as assessed by the investigator.

Patient incidence of the following AEs will be provided:

- Pre-treatment AEs by MedDRA System Organ Class (SOC), preferred term, dose and disease
- Treatment-emergent AEs by MedDRA SOC, preferred term, dose and disease
- Treatment-emergent AEs by MedDRA preferred term, dose and disease
- Treatment-related AEs by MedDRA SOC, preferred term, dose and disease
- Treatment-emergent AEs by MedDRA preferred term, maximum severity, dose and disease
- AEs leading to study discontinuation by MedDRA SOC, preferred term, dose and disease
- Treatment-emergent serious AEs (SAEs) by MedDRA SOC, preferred term, dose and disease
- Treatment-related SAEs by MedDRA SOC, preferred term, dose and disease
- AEs leading to death by MedDRA SOC, preferred term, dose and disease

In addition, the following analyses will be performed:

- Treatment-emergent AEs and treatment-emergent SAEs during the AE evaluation period will be summarized separately for patients with and without anti-drug antibody postdose.
- Treatment-emergent AEs that started or worsen in intensity after the AE evaluation period will be summarized with patient incidence by SOC, preferred term, disease group and dose level.
- Pre-treatment and treatment-emergent significant infections will be summarized by infection type which will be determined before database lock and will be documented in the CSR.

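### The transfusion subgroup is defined by the same condition that opens the transfusion limb of the response, so the Yes group has one more way to respond than the No group

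*SAP*

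**What the plan says.** SAP 2.1 (and, with the same rule, protocol 7.3.1) requires the platelet and LDH criteria together with "clinical benefit (either improvement in organ function or reduction in transfusion burden". Organ function has renal, pulmonary, neurological and gastrointestinal limbs. Freedom from transfusion is a further alternative, "only evaluated in patients who received transfusions within the 2 weeks prior to or on the first OMS721 dose date".

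SAP 2.8.2.1 counts a patient as a responder if the criteria are met "at any time post-baseline during the study". Under sensitivity analyses it then states: "Subgroup analyses for the following subgroups will be performed for the FAS population". One factor in that list is "Any transfusions within the 2 weeks prior to or on the first OMS721 dose date (Yes or No". No subgroup-specific endpoint is given, so the primary definition applies.

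The same list divides baseline platelet count at <20,000 / ≥20,000, as does SAP 3.2.3. The platelet response rule in SAP 2.1 changes at ≤20,000 / >20,000.

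**The concern.** The subgroup factor and the entry condition for one limb of the endpoint are the same thing. The two levels are scored on different sets of routes to response: any organ limb or the transfusion limb for Yes, any organ limb alone for No. Two otherwise identical groups of patients would have different expected response rates purely because of how the endpoint is written. A reader of the subgroup table could take a higher rate in transfused patients as better efficacy in that group, or take similar rates as consistency of effect, and neither reading would be sound.

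Nothing else planned supplies the missing comparison. The first alternative response (markers plus renal improvement) omits the transfusion limb, but is tabulated by dose and not by subgroup. The second removes only neurological function and keeps the transfusion limb.

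**Working it through.** **The plan's own precision figures.** SAP 1.3 gives exact 95% interval widths of 12.3% to 38.7% for 28 patients, and 30.6% to 69.4% at a 50% response. Clopper-Pearson limits for x = 0 to 28 give widths of 12.34% (x = 0 or 28) to 38.71% (x = 14), and 30.65% to 69.35% for 14/28. These agree and are not in dispute.

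**Inputs.** The documents give no value for any of the following, so all are assumptions:
- m = probability that the platelet and LDH criteria are met.
- o = probability that at least one organ limb is met, given the markers.
- t = probability that the transfusion limb is met, given the markers and no organ limb.

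The values m and o are taken as equal in the two subgroups, to isolate the effect of the definition.

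**Formulas.**
- P(response, Yes) = m × [1 − (1 − o)(1 − t)]
- P(response, No) = m × o
- Gap = m × (1 − o) × t

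The gap is above zero whenever m > 0, t > 0 and o < 1.

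**Central illustration** (m = 0.6, o = 0.4, t = 0.5):
- Yes: 0.6 × (1 − 0.6 × 0.5) = 0.42
- No: 0.6 × 0.4 = 0.24
- Gap: 0.6 × 0.6 × 0.5 = 0.18, or 18 points

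**Range** (m 0.5–0.7, o 0.3–0.5, t 0.3–0.5):
- Smallest: 0.5 × 0.5 × 0.3 = 0.075
- Largest: 0.7 × 0.7 × 0.5 = 0.245

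A wider grid (m 0.5–0.9, o 0.3–0.7, t 0.2–0.6) gives 3 points (38% against 35%) to 38 points (65% against 27%). The size depends heavily on the inputs; the direction at equal prognosis does not.

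**How easily it could be offset.** In the central illustration the clinical part is met with probability 0.70 for Yes and 0.40 for No, a ratio of 1.75. If the marker rate in Yes were 0.6 / 1.75 = 0.34 instead of 0.60, the two response rates would both be 24%. A larger deficit would reverse the sign.

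**Precision.** With an assumed 20/8 split and m = 0.7, o = 0.5, t = 0.4 (49% against 35%), the nearest whole counts are 10/20 and 3/8. Their exact 95% intervals are 27% to 73% and 9% to 76%.

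**With the transfusion limb removed at both levels**, both rates equal m × o, and the built-in gap is zero (24% against 24% in the central illustration).

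**The case against.** The best case for leaving the plan alone has several parts.

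- **The tables are descriptive.** No test between subgroups is planned, about 28 patients are expected, and the intervals above could not separate a 14-point gap from chance. This stands and limits the consequence. It does not make the two levels comparable, since imprecision and a difference in definition are separate problems.
- **The endpoint credits recovery of whatever was abnormal.** Coming off renal replacement therapy or a ventilator is also open only to patients who needed it, so multiple organ involvement carries a similar dependence. This is partly right. The transfusion factor differs because the subgroup condition and the entry condition are identical, and the limb can be removed cleanly at both levels.
- **The route to response can be rebuilt**, because SAP 2.8.2.1 lists each criterion by patient. True, but that would be a reconstruction after the fact and not a planned analysis.
- **The rule on confounding might deal with it.** Under that rule "the non-evaluable response criterion will not be included in the determination of responder". It concerns confounding factors, and the absence of a recent transfusion is not described as one. The SAP also does not say what happens to the clinical requirement when a No patient has no evaluable organ limb; dropping the requirement would favour No in those cases.

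Two stronger readings are tempting. A reader might infer that a difference in favour of transfused patients is bound to appear. The documents do not support that: counts on the day of a platelet transfusion or in the 2 days after it do not qualify, and transfused patients may be sicker, so the advantage could be masked or reversed.

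A reader might also infer that other factors in the list, such as "Significant infection (Yes or No", will count events after dosing, so that patients must survive long enough to enter the group. These factors carry no explicit time limit, but SAP 3.2.5 lists them as transplant history. Where SAP 3.4.1 means events after dosing it says so: "Pre-treatment and treatment-emergent significant infections will be summarized by infection type". Missing wording is not evidence that later events will be counted.

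**Conclusion.** The point holds as a matter of definition. At equal prognosis the Yes level has an advantage of m(1 − o)t: 18 points in the central illustration and 7.5 to 24.5 points over the assumed ranges, with no input taken from the documents. The extra limb matters only for patients who meet the markers and no organ limb. What is built in is an advantage, not the sign or size of the observed difference. As planned, the contrast cannot be read as a difference in drug effect in either direction.

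The primary conclusion is not touched: the 15% rule applies to the overall response rate in the FAS and PAS, and nobody's responder status changes.

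The platelet cut-point mismatch is real but small. It affects only a patient whose baseline average is exactly 20,000, who would be scored under the lower-count rule and shown in the higher-count group.

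**What to change.** 1. In SAP 2.8.2.1, for the transfusion subgroup, also report response defined as the TMA marker criteria plus any organ-function improvement, with freedom from transfusion removed at both levels. State that any reading of the Yes/No contrast rests on this version.
2. In SAP 2.8.2.1 and 3.2.3, set the platelet subgroup to ≤20,000 / >20,000 to match the response rule in SAP 2.1. The two levels will still be scored under different platelet rules; the change only makes the table agree with the rule.

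The cost is SAP wording and one extra subgroup run on data already collected. Protocol 13.2.5.1 mentions subgroup analyses without listing them, and protocol 13.2 asks for an amendment only when a principal feature changes, so SAP wording settled before the interim database lock should be enough. The small downside is that the rate in the added table will be lower than the primary rate, because one limb is missing; a footnote should say so.

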2.8.2.2. Secondary Efficacy Endpoints

2.8.2.2.1. 100-day Survival

The 100-day survival status will be determined as a binary variable. A patient achieves a 100-day survival if the overall survival from the date of HSCT-TMA diagnosis of the patient is greater

than or equal to 100 days. If the 100-day survival status of a patient is unknown (i.e., censored before 100 days), this patient will be considered to have died prior to 100 days. The 100-day survival rate will be estimated with exact 95% CI by dose for the FAS population.

In addition, cumulative incidence at 100 days for each of the pre-specified cause of death (GVHD, graft failure, infections, progression of underlying disease, HSCT-TMA and other) will be estimated by a competing risks analysis (Section 2.8.2.2.2).

2.8.2.2.2. Overall Survival

Overall survival will be calculated from the date of HSCT-TMA diagnosis. For the patients who are alive, their overall survival will be censored at the last known date of alive in the database. The method for handling a partially missing date of death is presented in Section 2.7.

Overall survival will be analyzed using Kaplan-Meier method by dose for the FAS population. Median overall survival and its 95% CI will be estimated by dose.

In addition, a competing risks analysis for overall survival will be performed. The cumulative incidence function of each pre-specified causes of death (GVHD, graft failure, infections, progression of underlying disease, HSCT-TMA, and others) will be estimated by nonparametric maximum likelihood method. The estimated cumulative incidence functions and their 95% CI will be displayed graphically.

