5. INTRODUCTION

5.1. Background

This study was originally designed to provide preliminary information on the safety and potential efficacy of OMS721 for the treatment of thrombotic microangiopathies (TMAs). As originally designed, this study included 3 types of TMA—hematopoietic stem cell transplant-associated TMA (HSCT-TMA), atypical hemolytic uremic syndrome (aHUS), and thrombotic thrombocytopenic purpura (TTP)—and included 2 stages: a dose-escalation stage and a cohort expansion stage. A separate Phase 3 study has been initiated for patients with aHUS (Study OMS721-HUS-002); therefore, patients with aHUS are no longer being enrolled in Study OMS721-TMA-001. Patients with TTP are also no longer being enrolled in this study because it was difficult to observe a treatment effect over the current standard of care.

Improvements in laboratory TMA markers have been observed in patients with HSCT-TMA in this ongoing study, and marked unexpected improvements were observed in some patients with life-threatening disease. In support of an application for Breakthrough Therapy Designation (BTD) from the United States Food and Drug Administration (FDA), Omeros Corporation (Omeros, Sponsor) compared survival in OMS721-treated patients with a literature-based historical control. A substantial survival improvement was observed, and BTD was granted by FDA for the treatment of patients with HSCT-TMA who have persistent TMA despite modification of immunosuppressive therapy. The Sponsor has had continued discussions with regulatory agencies internationally regarding approval of OMS721 for the treatment of HSCT-TMA. These discussions have focused on approval based on patients with HSCT-TMA treated in this study as well as patients with HSCT-TMA treated under compassionate use or expanded-access protocols. Efficacy will be assessed by response to treatment evaluated by organ function or transfusion burden and laboratory measures of TMA.

Amendment 11 of this protocol provides for collection of additional data for OMS721-treated patients with HSCT-TMA to determine patient responses and longer-term outcomes and to support marketing authorization applications. The additional data to be collected are limited to patient demographics and baseline conditions, donor characteristics, the transplant procedure, concomitant medications, TMA-related laboratory measures, transfusions, transplant complications, and outcomes (see Section 19.4 for additional detail).

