[Khosla 2017]. Plasma therapy is thought to have no utility in this patient population [Khosla 2017, Rosenthal 2016]. Patients who do not respond to modification of their immunosuppression have a poor prognosis. Adult mortality has been reported to be as high as 100% (4 out of 4 patients, all of whom died within 69 days from diagnosis) [Worel 2007]. In a larger and more recent series, only 17% of adult patients (4 out of 24) who underwent immunosuppression modification and received treatment with plasmapheresis, defibratide, or rituximab survived 1 year [Bohl 2017]. Eculizumab has been reported to treat HSCT-TMA effectively with a 90% response rate when used off-label in 1 adult study; however, there was a high rate of infection-related mortality following eculizumab treatment [Bohl 2017]. These data demonstrate that HSCT-TMA is a life-threatening condition and, with the lack of effective treatment options, represents a significant unmet medical need.

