13.2.1.2. Analysis Populations

Efficacy analyses will be performed for the Full Analysis Set (FAS) population and the Per-protocol Patient Set (PAS) population. The FAS population will include all HSCT-TMA patients who received any amount of study drug. The PAS population will include all HSCT-TMA patients who received at least 4 weeks of study treatment (treatment period is ≥ 28 days).

Safety analyses will be based on the Safety Analysis Set population, which includes all patients (aHUS, TTP, and HSCT-TMA) who received any amount of study drug.

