13.2.5.2. Analysis of Secondary Efficacy Endpoints

The 100-day survival status will be determined as a binary variable. A patient achieves a 100-day survival if the overall survival from the date of HSCT-TMA diagnosis of the patient is ≥ 100 days. If the 100-day survival status of a patient is unknown (i.e., censored before 100 days), this patient will be considered to have died prior to 100 days. The 100-day survival rate will be estimated with exact 95% CI by dose for the FAS population.

Overall survival will be calculated from the date of TMA diagnosis. Overall survival will be analyzed using Kaplan-Meier method by dose for the FAS population. Median overall survival and its 95% CI will be estimated by dose.

The duration of response will be estimated for the FAS population. Duration of response is defined as the number of days from the first response date to the first relapse date (first relapse date – first response date + 1). The first response date is the first date that platelet count and LDH response is achieved. Relapse is defined as having a platelet count greater than 50% decrease from the maximum platelet count and an LDH greater than 1.5 times the ULN. Relapse will be evaluated using the platelet count and the LDH collected within 1 week. Duration of response will be censored at the last platelet or LDH collection date if relapse does not occur during the study. Kaplan-Meier analysis of the duration of response will be performed for the patients who achieve a response by dose for the FAS population. Median duration of response will be presented with 95% CI.

Binary secondary efficacy endpoints will be summarized with exact 95% CI by dose for the FAS population. Non-responder imputation will be used to handle missing data.

CONFIDENTIAL

No use, disclosure or reproduction outside of Omeros without prior written authorization

In addition, efficacy laboratory values of platelet count, LDH, creatinine, hemoglobin, and haptoglobin will be plotted over time for the HSCT-TMA patients.

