3.2.4. Thrombotic Microangiopathy History

TMA history will be summarized with descriptive statistics by dose and disease for the safety population:

- Time (months or years) from TMA diagnosis to Day 1
- Time from HSCT to TMA diagnosis (HSCT-TMA only)
- Total number of previous episodes of TMA
- Time (days or months) from the onset of the current TMA episode to Day 1
- Shiga-toxin producing *E. Coli* test for current TMA episode (positive or negative for a-HUS patients only)
- Direct coombs test for current TMA episode (positive or negative)
- Most recent ADAMTS13 test result prior to dosing (historical data is allowed)
- Any transfusions within the 2 weeks prior to or on the first OMS721 dose date (Yes or No, HSCT-TMA only)
- Other risk factors for the HSCT-TMA patients will be identified after review of their historical data.

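### Survival is timed from HSCT-TMA diagnosis in patients selected for having been dosed, so any wait before the first dose counts as guaranteed survival, and no survival from first dose is planned

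*SAP*

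**What the plan says.** Both documents start overall survival at diagnosis. Protocol 13.2.5.2: "Overall survival will be calculated from the date of TMA diagnosis". SAP 2.8.2.2.2: "Overall survival will be calculated from the date of HSCT-TMA diagnosis". The binary endpoint in SAP 2.8.2.2.1 follows the same clock: "A patient achieves a 100-day survival if the overall survival from the date of HSCT-TMA diagnosis of the patient" is at least 100 days. If status at 100 days is unknown, "this patient will be considered to have died prior to 100 days". Overall survival uses ordinary Kaplan-Meier estimation; the 100-day rate is a proportion with an exact 95% interval.

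Both are run in the Full Analysis Set, defined in Protocol 13.2.1.2 (and likewise in SAP 2.2): "The FAS population will include all HSCT-TMA patients who received any amount of study drug".

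The other survival analyses are competing risks by cause of death (SAP 2.8.2.2.1 and 2.8.2.2.2) and a split by responder status (SAP 2.8.2.2.5). Neither states a different time origin. The interval in question appears only as a baseline descriptor in SAP 3.2.4, "Time (months or years) from TMA diagnosis to Day 1", and nothing links it to the survival estimates. Protocol Table 2 (Section 19.4) takes the diagnosis date as the first chart record of HSCT-TMA. If the day of that date is missing, SAP 2.7 sets it to the first of the month.

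**The concern.** Entry to the analysis requires surviving from diagnosis to the first infusion, but the clock starts at diagnosis. Everyone in the set is alive throughout that interval by construction. The curve is flat over it, and the 100-day rate counts it as survival achieved. A patient first dosed 100 days or more after diagnosis is a certain 100-day success. Setting a missing diagnosis day to 1 can only lengthen the interval, by up to 30 days in a 31-day month.

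This matters because the study is uncontrolled, so readers will judge its survival figures against other series. Protocol 5.1 reports that, for a designation request, the sponsor "compared survival in OMS721-treated patients with a literature-based historical control". One background series in Protocol 5.1.2.3 is described as "4 out of 4 patients, all of whom died within 69 days from diagnosis". A treated-only figure timed from diagnosis, set beside a series of all diagnosed patients, would credit the drug with time before it was given.

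**Working it through.** **Inputs.** The time origin, analysis set and missing-status rule are as above. The number of HSCT-TMA patients is 2 + 22 + 4 = 28 (SAP Table 1), 4 of them at 370 mg. The lag from diagnosis to first dose is not given, so it is varied here as an assumption.

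**The plan's own figures.** Clopper-Pearson limits for n = 28 give interval widths from 12.3% (0 or 28 events) to 38.7% (14 events), and 14/28 gives 30.6% to 69.4%. These match Protocol 13.1 and SAP 1.3. No stated number is disputed.

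**Effect of a common lag, constant hazard.** Let S be 100-day survival from diagnosis if deaths before dosing could be counted, and d the lag in days. Given survival to day d, the planned analysis estimates

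S(100 | alive at d) = S^(1 − d/100).

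For S = 0.50: 0.50^0.93 = 0.525, 0.50^0.86 = 0.551, 0.50^0.72 = 0.607.

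| True S | d = 0 | d = 7 | d = 14 | d = 28 |
|---|---|---|---|---|
| 40% | 40.0% | 42.6% | 45.5% | 51.7% |
| 50% | 50.0% | 52.5% | 55.1% | 60.7% |
| 60% | 60.0% | 62.2% | 64.4% | 69.2% |

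In 28 patients with S = 50%, expected 100-day survivors rise from 14.0 to 28 × 0.551 = 15.4 (14 days) or 28 × 0.607 = 17.0 (28 days). The exact interval for 17/28 is 40.6% to 78.5%. Under the same assumptions, median survival from diagnosis equals the median from first dose plus d: 100 days becomes 114 or 128.

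**If half the patients have no lag.** 0.5 × 0.50 + 0.5 × 0.50^(1 − d/100) gives 51.2%, 52.5% and 55.4% when the other half have 7, 14 or 28 days.

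**If the hazard is higher early after diagnosis.** With a Weibull shape of 0.7 (an assumption), 0.50^(1 − (d/100)^0.7) gives 55.7%, 59.6% and 66.4% for 7, 14 and 28 days.

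**If the early-heavy hazard starts at first dose instead.** Take 100-day survival from first dose as 50% and a Weibull shape of 0.5. The diagnosis-origin rate is then 0.50^(((100 − d)/100)^0.5): 52.6% for 14 days and 55.5% for 28.

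**Opposing rule.** Each patient who is in fact alive at day 100 but has unknown status lowers the binary rate by 1/28 = 3.6 points. This applies to the binary rate only; Kaplan-Meier survival censors such patients at the last date known alive (SAP 2.8.2.2.2).

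**The case against.** **Survival carries little formal weight.** Efficacy is judged on response, with a 15% lower bound. Survival is secondary and descriptive, with no threshold. The statement that about 28 patients will support approval leads into the precision of the response rate, not of survival. This stands, and it limits the weight of the point.

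**Diagnosis is a sensible origin.** It matches the one background series with a stated origin, and first-dose survival answers a different question. This also stands, so the planned endpoints should remain. But matching the origin does not match the population: here every patient had to live long enough to be dosed.

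**The lag may be small.** A reader might infer that the persistence criterion or the screening period forces a wait of two to four weeks. The documents do not support that. Protocol 8.1 also allows entry at 30 days or more after transplant, Protocol Table 2 notes that immunosuppression may be modified before the chart diagnosis, and 28 days is a maximum for screening. The lag could be near zero for some patients.

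**Other rules pull the other way.** Unknown 100-day status counts as death, and a death date lacking only its day is set to the first of the month. These may offset part of the shift but do not remove the guaranteed time.

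**The interval is partly covered already.** SAP 3.2.4 also plans the time from onset of the current episode to Day 1, with days as an option. Onset and diagnosis are collected as separate dates, so this is related information but not the interval needed.

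**Conclusion.** The structural point is established: the origin is diagnosis, the set is treated-only, and no survival from first dose is planned. The redacted SAP block before Section 2.8.4 is unlikely to change this, since SAP 3.3 ties Section 2.8.3 to pharmacokinetics, pharmacodynamics and immunogenicity. As a measure of survival from diagnosis, the guaranteed time can only raise the figures.

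Its size is not established. The illustration of 2.5 to 10.7 points at a true 50% rests on assumed lags of 7 to 28 days common to all patients and a constant hazard. With no lag there is no effect. Against sampling error in 28 patients the shift is modest, but the exact interval does not allow for it.

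Two stronger readings go too far. A reader might conclude that survival will be overstated relative to all diagnosed patients. That does not follow: enrolment requires persistent disease, while Protocol 7.1 says HSCT-TMA often resolves within weeks of changing the calcineurin inhibitor, so the enrolled group may otherwise have a worse outlook. The exclusion of life expectancy under 3 months selects in the opposite direction. The net direction is unknown. A reader might also conclude that the historical comparison was biased by this. The documents identify neither the control series nor its time origin, and they plan no new external comparison.

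**What to change.** Keep the planned endpoints and add the following:

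1. In SAP 2.8.2.2.1 and 2.8.2.2.2, add overall survival and day-100 survival from the first OMS721 dose for the Full Analysis Set, by dose and with both doses combined, since only 4 patients had 370 mg. Estimate both by Kaplan-Meier and use the chart vital status that Protocol Table 2 already collects. The last scheduled visit, Day 92, is 92 − 1 = 91 days after first dose, so visit data alone would fall short of 100 days.
2. In SAP 3.2.4, report the diagnosis-to-Day 1 interval in days for HSCT-TMA patients.
3. Label the diagnosis-origin estimates as conditional on surviving to first dose.

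Kaplan-Meier from diagnosis with delayed entry at first dose can be an optional sensitivity analysis, pooled across doses and with numbers at risk shown. It should not replace the plan: it assumes the lag is independent of prognosis, and few patients may be at risk early on.

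The cost is SAP wording and one more survival run on dates already collected. The downsides are possibly less favourable figures, more estimates from about 28 patients, and a first-dose estimate that does not match a diagnosis-origin comparator and still leaves the life-expectancy selection in place.
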